### **2.5.4 Sensitivity analyses 1**

Robustness of the primary efficacy results will be explored by multiple imputation assuming MAR i.e., missing at random algorithm to impute missing values in the primary analysis, except the Baseline value. Baseline value will not be imputed.

To investigate the sensitivity of the analysis results based on the MAR assumption, we will perform an analysis using a pattern mixture model approach which assumes, besides the imputation with 0 for the NT-proBNP values after death. This sensitivity analysis would first create multiple (100) imputations of missing NT-proBNP values under a MAR assumption, resulting in multiple (100) complete data sets. The imputation model assumes a multivariate normal model for the 3 NT-proBNP measurements at baseline, Week 4 and Week 8. To the resulting 100 datasets, the original analysis model described above will be fitted, yielding 100 sets of parameter estimates and associated covariance matrices. These are then combined by using Rubin's rules to derive overall estimates, and confidence intervals that adequately reflect missing data uncertainty as well as associated p-values.

The sensitivity analysis to address the primary objective will be based on the same primary estimand.

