12.4.2 Handling of missing values/censoring/discontinuations

The analysis will be performed based on all available data in the FAS. Missing values caused due to unevaluable samples or early discontinuations will not be imputed. If either the baseline value or both Weeks 4 and 8 are missing, then the patient will not be included in the analysis.

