##### **Estimand 1**

Population: Defined through the appropriate inclusion/exclusion criteria to reflect the targeted study population currently hospitalized for or within 30 days of a WHF event (HFpEF decompensation). A WHF event (HFpEF decompensation) is defined as a hospitalization, emergency department (ED) visit or out-of-hospital urgent HF visit, all requiring IV diuretics.

Endpoint: Time-averaged proportional change between Baseline and weeks 4 and 8 in NT-proBNP

Treatment: The randomized treatment sacubitril/valsartan or valsartan

Intercurrent event: Using a treatment policy strategy to handle the intercurrent event of treatment discontinuation.

Summary measure: Difference between treatment in ratios of geometric means

The primary null hypothesis to be tested is the ratio of the geometric means of NT-proBNP (average of Weeks 4 and 8 divided by Baseline) for the sacubitril/valsartan and valsartan treatment groups are equal ( $H_{10}$ ) versus the alternative hypothesis that the ratio of the geometric means of NT-proBNP are not equal ( $H_{1a}$ ).

For NT-proBNP, the time-averaged proportional change from Baseline in a natural logarithmic scale will be analyzed using an ANCOVA model using data from Weeks 4 and 8 with treatment,

in-hospital/out-of-hospital randomization status, gender, and Baseline LVEF ( $\leq$  Median,  $>$  Median) as fixed effect factors, age and the logarithmic Baseline NT-proBNP as covariates.

The values from Weeks 4 and 8 will be averaged and the change from Baseline in log transformed NT-proBNP will be calculated as follows:

$$\ln(\text{average post dose value}) - \ln(\text{baseline value})$$

The estimated treatment effect in terms of ratios of geometric means, based on the least-squares (LS) means from the model, and the corresponding two-sided 95% confidence intervals (CIs) will be presented.

The geometric means (presented as a ratio to Baseline) will be calculated by exponentially back transforming the LS means based on the ANCOVA model as follows:

$$\exp(\text{LS mean})$$

The FAS will be used for the primary endpoint analysis.

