## **2.6.2 Statistical hypothesis, model, and method of analysis**

### **2.6.2.1 Analysis of secondary endpoint 1**

The composite hierarchical outcome consisting of below 4 variables

- a) time to CV death (Adjudicated by EAC),
- b) number and times of HF hospitalizations during follow-up (Adjudicated by EAC - only the confirmed events will be considered, i.e. HF hospitalizations meeting PARAGLIDE-HF criteria),
- c) number and times of urgent HF visits during follow-up (Adjudicated by EAC), and
- d) time-averaged proportional change in NT-proBNP (from baseline to Weeks 4 and 8)

This secondary efficacy endpoint of the composite hierarchical outcome will be analyzed estimating the unmatched win ratio by comparing every participant in the sacubitril/valsartan arm to every participant in the valsartan arm to determine a winner (unmatched pairing method). The estimated win ratio (the total number of wins in the sacubitril/valsartan arm divided by the total number of wins in the valsartan arm) will be calculated. The corresponding null and alternative hypotheses are:

$H_{20}$ : Win ratio is equal to 1, versus

$H_{2a}$ : Win ratio is not equal to 1.

A win ratio greater than 1 will be in favor of sacubitril/valsartan arm. The testing of hypothesis  $H_{20}$  and calculation of the corresponding two-sided 95% CIs will be performed.

A component will only be used as tie-breaker in the pairwise comparison between two subjects if the comparison of components with a higher priority resulted in a tie. For component a) the subject with the later time to CV death is the winner. For component, b) the subject with the smaller number of HF hospitalizations in time at risk that is common for both subjects (for definition see Section 2.6.2.1.1) is the winner. If the number of HF hospitalizations in the time at risk is common for both subjects it is tied, the subject with the later time of the last HF hospitalization is the winner. For component c) the same algorithm is applied as for component b). For component d), the subject with the larger decrease or smaller increase in the proportional change is considered a winner; if the ratio of the proportional changes from two subjects is between 0.75 and 1/0.75, then the pairwise comparison of the change in NT-proBNP is considered tied. This proportional change is equivalent to  $\pm 0.2876$  on the natural log scale  $\ln(0.75)$  and  $\ln(1/0.75)$ .

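### SAP 2.5.4, read literally, sets NT-proBNP to 0 after death and then takes logs, so the pattern-mixture analysis scores death as benefit or leaves it undefined and cannot test MAR

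*SAP*

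**What the plan says.** SAP 2.5.4 has two parts. The first paragraph describes multiple imputation under MAR, with baseline not imputed. The second describes a pattern-mixture analysis to examine how far the result depends on MAR. The sentence that should name its assumption contains the words "besides the imputation with 0 for the NT-proBNP values after death" and ends without saying what else is assumed.

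The steps that follow create 100 imputed datasets under MAR: "The imputation model assumes a multivariate normal model for the 3 NT-proBNP measurements at baseline, Week 4 and Week 8". Then, "To the resulting 100 datasets, the original analysis model described above will be fitted", and the results are pooled by Rubin's rules. The section adds: "The sensitivity analysis to address the primary objective will be based on the same primary estimand".

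The model being refitted is in SAP 2.5.2: "The values from Weeks 4 and 8 will be averaged and the change from Baseline in log transformed NT-proBNP will be calculated as follows", namely ln(average post-dose value) - ln(baseline value). Protocol 12.4.1 confirms that the arithmetic mean is taken before the log. On who enters the primary analysis, Protocol 12.4.2 says: "If either the baseline value or both Weeks 4 and 8 are missing, then the patient will not be included in the analysis". The primary estimand names one intercurrent event: "Using a treatment policy strategy to handle the intercurrent event of treatment discontinuation". It has no rule for death.

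The direction of benefit is not in doubt. The sample size targets a 23% reduction, and in the NT-proBNP component of the win ratio "the subject with the larger decrease or smaller increase in the proportional change is considered a winner".

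**The concern.** A zero concentration cannot be logged, and averaging a zero with a measured value halves that value. In an endpoint where a fall is the desired result, both consequences are wrong for a patient who has died. One gives no usable outcome; the other records an improvement that did not occur. The error favours whichever arm has more deaths.

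This part of 2.5.4 is the plan's only stated test of MAR for the primary endpoint. If its one departure from MAR points the wrong way, agreement with the primary result offers no reassurance and disagreement cannot be interpreted. The same SAP treats CV death as the worst outcome at the top of the win-ratio hierarchy, so the two analyses would score the same patient in opposite directions.

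**Working it through.** **Inputs.** Zero after death, and refitting of the primary model: SAP 2.5.4. Outcome formula: SAP 2.5.2 and Protocol 12.4.1. Exclusion rule for missing visits: Protocol 12.4.2. From SAP section 3: design effect -0.2614, SD 0.85, 15% missing, 450 patients randomised 1:1 (225 per arm).

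**The plan's own figures.** ln(0.77) = -0.2614, as stated. For power, 450 × 0.85 = 382.5 patients, about 191 per arm. With SD 0.85 and two-sided 0.05 this gives 0.852, which reproduces the stated 85%. SAP 2.5.4 states no numerical result of its own.

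**Death between Weeks 4 and 8.** Write B for baseline and W4, W8 for the two visits.

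- Primary analysis: only Week 8 is missing, so the patient stays in on Week 4 alone: ln(W4) - ln(B).
- SAP 2.5.4 with W8 = 0: ln((W4 + 0)/2) - ln(B) = ln(W4) - ln(B) + ln(0.5).
- Difference: ln(0.5) = -0.693, whatever the values of B and W4.
- Relative to the design effect, for that one patient: 0.693 / 0.2614 = 2.65.

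Illustrations with chosen values: B = 1000 and W4 = 700 moves from a ratio of 0.70 to 0.35. B = 1000 and W4 = 1500, a 50% rise, moves from 1.50 to 0.75 and is recorded as a 25% fall.

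**The same death against a MAR-imputed Week 8 value.** If MAR would have imputed W8 = r × W4, the zero multiplies the average by 1/(1 + r):

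| r | Extra fall |
|---|---|
| 0.5 | 33% |
| 1 | 50% |
| 2 | 67% |

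The size depends on r, but for any positive r the movement is downward.

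**Death before Week 4.** (0 + 0)/2 = 0, and ln(0) is undefined. The patient either drops out, as in the primary analysis where both visits are missing, or needs a floor. The SAP gives no floor, offset or other rule.

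**If the 0 were meant on the log scale.** That is 1 pg/mL. An early death then scores -ln(B), which is -6.2 to -8.3 for an assumed baseline of 500 to 4000 pg/mL. A Week 4-8 death scores almost as before: with B = 1000 and W4 = 700, ln(701/2) - ln(1000) = -1.048, against -0.357 in the primary analysis. Death still counts as a fall.

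**Effect on the treatment comparison.** Per net Week 4-8 death (the excess in one arm), taking all 225 patients in the arm as analysed because missing weeks are imputed:

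- -0.693 / 225 = -0.0031 on the arm mean.
- 0.0031 / 0.2614 = 1.2% of the design effect.

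The documents give no death count by Week 8. For an assumed 1 to 5 net deaths the shift is -0.003 to -0.015, or 1.2% to 5.9% of the design effect.

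**What remains of the MAR test.** Every listed step (imputation, refitting, pooling) is a MAR step. Without the zero, nothing stated departs from MAR.

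**The case against.** The strongest reply is that the source sentence is unfinished. It names the zero only in passing, the numbered-out procedure never uses it, and its scale is not given. Text may have been lost, although no redaction is marked there. On that view the section is incomplete rather than wrong.

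Part of this stands: the authors' intention is uncertain, and the point is about the literal text. But the literal text refers to the NT-proBNP values themselves, and the log-scale reading has the same direction. Only an unstated reading, with 0 meaning no change from baseline, escapes the problem. A lost clause would not rescue the zero either, because the sentence presents the zero as additional to whatever else is assumed. If the zero is never applied, the analysis is plain MAR imputation and still tests nothing.

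It is also fair to say that the numerical effect is small, that no decision rule depends on 2.5.4, and that the win ratio already ranks CV death as worst. All of this stands and limits the importance of the point. The win ratio is not, however, a check on MAR for the primary endpoint.

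A reader might infer that every late death is credited with exactly a further 50% fall. That is exact only against the value in the primary analysis. A reader might also infer that early deaths would be scored as enormous reductions. On the literal text they have no defined outcome; a large credit requires either a floor that the SAP does not state or the log-scale reading. Finally, a reader might infer that imputation would produce negative concentrations. The SAP does not say that the multivariate normal model is on the raw scale, so the missing scale and the unstated role of treatment arm are gaps, not errors.

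**Conclusion.** The point holds for the second paragraph of SAP 2.5.4 as literally written. A Week 4-8 death is placed 0.693 log units below its primary-analysis value, and an earlier death has no defined outcome. Because lower is better, the only stated departure from MAR counts death as benefit, so the analysis cannot serve its stated purpose. The claim to share the primary estimand is also unsupported, since that estimand has no rule for death and assigning a value to death is a different strategy.

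The expected numerical effect is small, about 1.2% of the design effect per net Week 4-8 death. This assumes 225 analysed patients per arm, a raw-scale zero, and that a patient with Week 4 only enters the primary analysis on that value. The fault lies in direction and interpretability, not size.

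It would be wrong to conclude that the trial's main result is biased. The primary analysis imputes nothing, and the zero is not stated for the MAR analysis in the first paragraph of 2.5.4 or for Sensitivity analyses 2 to 4. The stated power is also unaffected. The section should be corrected, but the point is of modest weight.

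**What to change.** In SAP 2.5.4:

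1. Delete the imputation with 0.
2. Complete the pattern-mixture sentence with a stated departure from MAR in the unfavourable direction on the log scale, for example a delta-adjusted shift toward higher ln(NT-proBNP).
3. State that ln(NT-proBNP) is imputed, with treatment arm in the imputation model.
4. State post-death handling so that death is never scored as a reduction. Either do not impute after death, or assign an unfavourable value and label that a supplementary composite-strategy analysis rather than one on the same primary estimand.

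The delta adjustment is one reasonable choice among several. What is needed is a named, unfavourable departure and an explicit rule for deaths. The cost is SAP wording and a few lines of imputation code before database lock, with no new data.

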### **2.5.3 Handling of missing values/censoring/discontinuations**

The analysis will be performed based on all available data in the FAS. Missing values caused due to unevaluable samples or early discontinuations will not be imputed.

Also, NT-proBNP from unscheduled visits will not be used for the analysis.

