#### **Sample size for the primary endpoint**

This sample size of 450 subjects would have 85% power to detect a 23% reduction in the geometric mean of the proportional change from Baseline to an average of Weeks 4 and 8 in NT-proBNP for the sacubitril/valsartan treatment group. This 23% reduction in geometric mean is equivalent to -0.2614 in natural log scale ( $=\ln(0.77)$ ). The power is estimated assuming a two sided significance level of 0.05, a common SD of 0.85 for change in log transformed NT-proBNP and a 15% rate of missingness in NT-proBNP at baseline or at both Week 4 and Week 8.

nQuery Version 8.4.1.0 (2019) software package is used in calculating the power of the test.

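### Sensitivity analysis 1 is meant to test the missing-at-random assumption but, as written, states no departure from it except after death

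*SAP*

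**What the plan says.** The primary analysis is an ANCOVA on all available data. On missing values, SAP 2.5.3 states: "Missing values caused due to unevaluable samples or early discontinuations will not be imputed". Protocol 12.4.2 adds that a patient without a baseline value, or without both the Week 4 and Week 8 values, is left out.

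SAP 2.5.4 has two parts. The first plans multiple imputation under MAR for everything except the baseline. The second is introduced as a test of that assumption: "To investigate the sensitivity of the analysis results based on the MAR assumption, we will perform an analysis using a pattern mixture model approach". The sentence goes on to say what the model assumes, mentions only that NT-proBNP is set to 0 after death, and stops. The steps then begin: "This sensitivity analysis would first create multiple (100) imputations of missing NT-proBNP values under a MAR assumption". They use a multivariate normal model for the three NT-proBNP measurements. The primary ANCOVA is fitted to each completed data set and the results are combined by Rubin's rules.

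The sample-size section allows for "a 15% rate of missingness in NT-proBNP at baseline or at both Week 4 and Week 8".

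**The concern.** A pattern-mixture check of MAR needs a stated way in which unobserved values differ from what MAR predicts, such as a shift, a draw from the control arm or a pattern-specific parameter. None appears for patients who are alive. The wording implies that something follows the first step, but nothing that follows changes the imputed values. For living patients the second part therefore repeats the first.

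This matters because the complete-case ANCOVA also relies on MAR given its covariates. Two analyses that share an assumption cannot show what happens when it fails, and their agreement could be mistaken for robustness.

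The documents give reasons to ask the question. After treatment discontinuation, the minimum data in Protocol 9.1.1 are concomitant treatments and adverse events, not NT-proBNP. SAP 2.11 says that samples from patients who withdrew consent will not be analysed centrally. The win-ratio text in Protocol 12.5.1 discusses NT-proBNP missing because of CV death or after heart failure events. The described imputation model contains neither heart failure events nor discontinuation status.

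**Working it through.** **1. Is a departure specified elsewhere?**
- SAP 2.5.5 restricts the analysis to patients recruited under the amendments, without imputation.
- SAP 2.5.6 drops assessments after a positive COVID-19 status, without imputation.
- SAP 2.5.7 splits patients by enrollment window, without imputation.
- Protocol 12.4.3 says only that multiple imputation will be considered.

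No readable analysis of the primary endpoint departs from MAR for missingness other than death.

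**2. Reproduce the planned power.** Inputs from the SAP sample-size section: 450 patients at 1:1, 85% power, "a two sided significance level of 0.05", ln(0.77) = -0.2614, "a common SD of 0.85 for change in log transformed NT-proBNP" and 15% missing.
- Evaluable per arm: 450 × 0.85 / 2 = 191.25.
- SE = 0.85 × √(2/191.25) = 0.0869.
- Power is 85.2% by the normal approximation and 85.0% by the noncentral t with 191 per arm. The stated 85% reproduces.
- 95% CI if the observed ratio is 0.77: exp(-0.2614 ± 1.96 × 0.0869) = 0.65 to 0.91.

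**3. What a departure would do.** Assume the SE stays at 0.0869 and that only missing sacubitril/valsartan patients, a fraction f of the arm, are k-fold worse than MAR predicts. The effect becomes ln(0.77) + f × ln(k). Significance is lost when ln(k) = (0.2614 - 1.96 × 0.0869)/f = 0.0910/f.

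| f | k at which significance is lost | ratio at k = 1.5 | ratio at k = 2 |
|---|---|---|---|
| 15% | 1.83 | 0.818 | 0.854 |
| 10% | 2.48 | 0.802 | 0.825 |
| 5% | 6.17 | 0.786 | 0.797 |

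At an assumed observed ratio of 0.80 with f = 15%: ln(k) = (0.2231 - 0.1704)/0.15 = 0.351, so k is about 1.4.

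**4. Jump to reference.** If all 15% respond like valsartan patients, the effect is 0.85 × (-0.2614) = -0.222, a ratio of about 0.80. Then z = 0.222/0.087, about 2.55, which is still significant.

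**5. Would the described steps reveal a departure?** Simulation with 225 per arm, 15% missing both visits, 300 runs and 20 imputations. Treatment and baseline were in the imputation model. Assumed log-scale SDs were 0.9 (baseline), 0.75 (between patients) and 0.4 (within visit).

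| Missing active-arm patients | Full data | Complete case | MAR imputation | MAR plus the true delta |
|---|---|---|---|---|
| as MAR predicts | 0.772 | 0.770 | 0.770 | 0.770 |
| 1.5-fold worse | 0.815 | 0.764 | 0.764 | 0.812 |
| 2-fold worse | 0.855 | 0.771 | 0.771 | 0.856 |

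MAR imputation and complete case differed by about 0.006 on the log scale on average. MAR imputation followed the complete-case answer whether or not MAR held.

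**The case against.** The strongest reply is that this is a drafting gap. The sentence on the model's assumption has lost its object and the steps imply a sequel, so a departure may have been intended. That stands: a reader might infer that the sponsor decided against any departure, and the text does not show this. But no redaction mark appears there, and the listed steps run to completion without a departure, so a programmer following them would apply none.

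Three stronger readings also fail:

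- *About 68 patients are affected.* This is a ceiling (15% of 450 = 67.5). The 15% includes missing baselines, which are never imputed, and may include deaths.
- *Patients who stop drug are assumed to keep its full effect.* The estimand is treatment policy. Protocol 9.1.1 asks patients who stop drug to return where possible, and Protocol 6.4.1 seeks NT-proBNP after stopping. Observed values can therefore include off-drug ones, and imputation by arm would reflect that mixture. The narrower worry stands: patients who stop and are not sampled are treated like those who are sampled.
- *A plausible departure would overturn the result.* At the planned effect, jump to reference for the whole 15% does not.

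The SAP says only that robustness will be explored, so a claim of proven robustness would be a prediction. MAR imputation can also differ slightly from the primary result by filling a single missing week, but that does not test MAR. The rule for deaths is a departure, but 0 is the lowest possible NT-proBNP value, so it is not a stress test. It also leaves the logarithm undefined if both weeks are 0, which needs clarifying.

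**Conclusion.** The point holds. SAP 2.5.4 announces a test of MAR and describes steps that cannot perform one for patients missing for reasons other than death. No other readable analysis does so. The primary analysis itself is not invalidated.

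The size is moderate and depends on quantities the documents do not give. With the full 15% missing and the planned ratio observed, missing sacubitril/valsartan patients would have to be about 1.83-fold worse than MAR predicts for significance to be lost. A lower share of imputable patients moves that point away, and a smaller observed effect moves it closer. These figures assume a fixed SE and a common shift in every missing active-arm patient, with none in the valsartan arm. The shift sizes, the 10% and 5% shares, the ratio of 0.80 and the simulation SDs are illustrative assumptions.

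**What to change.** In SAP 2.5.4, complete the sentence and state the departure.

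1. Keep the 100 MAR imputations as step 1, and say that treatment arm is in the imputation model. The text does not say so now; leaving it out would pull the arms together for a reason unrelated to any stated departure.
2. Redraw the missing Week 4 and Week 8 values of sacubitril/valsartan patients who stopped drug from the valsartan-arm distribution, then refit and pool. This group is smaller than the whole 15% used in the jump-to-reference figure above.
3. Add a delta to the imputed ln NT-proBNP values in the sacubitril/valsartan arm, starting at 0 and increasing until the 95% CI for the ratio first includes 1. Do not cap it at ln 2: at 10% missing the tipping point is 2.48-fold, beyond that limit.
4. Report that delta with the number of patients imputed per arm, so that readers can judge whether it is plausible.

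Control-based and delta methods are not the only acceptable departures, but one must be written down before unblinding. The cost is SAP wording and a small amount of code after the imputation step, with no new data.

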8.3.3 Biomarkers

BNP or NT-proBNP will be measured in all patients by using the local laboratory at Visit 1 to determine eligibility. NT-proBNP will be measured in all patients using the central laboratory at Visits 2 (randomization), 3, 5, and 7 (Weeks 0, 1, 4, and 8 respectively).

During the COVID-19 pandemic that limits or prevents on-site study visits, or if visits by site staff to a participant's home are not feasible, the collection of standard chemistry and hematology samples may be modified by Novartis and will be communicated to the Investigator. For the primary endpoint biomarkers (Weeks 4 and 8), alternative methods of collecting and ensuring shipment of biomarkers to the central laboratory should be implemented. Alternative methods must comply with guidance issued by local regulatory bodies and be discussed with Novartis.

Evaluation of neprilysin measurement at baseline as a predictor of clinical outcome may be added depending on availability of a validated assay and sample handling requirements. The list may be changed or expanded further as new relevant biomarkers may be discovered during this study and after its completion. As such, serum and plasma will be bio-banked for analysis of yet to be identified diagnostic biomarkers. Details of sample collection, handling and shipment will be provided to investigators in the laboratory manual.

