## **2.11 Biomarkers**

NT-proBNP will be collected and descriptively summarized by visit, treatment group. NT-proBNP will be measured in all subjects using the central laboratory at Visits 2 (randomization), 3, 5, and 7 (Weeks 0, 1, 4, and 8 respectively). Values and the change from Baseline for each parameter will be summarized by visit and treatment group. Analyses will be based on the FAS.

NT-proBNP values will be based on clinical laboratory samples processed and assessed by the central laboratory.

[figure not shown]

P  
D

Additional analysis of biomarkers is discussed in Protocol [Sections 2.5, 2.7, and 2.13](#).

Biomarker samples from subjects who withdrew consent will not be analyzed by the central laboratory.

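### The SAP's imputation model for missing Week 4 and Week 8 NT-proBNP names neither the randomized arm, nor Week 1, nor the ANCOVA covariates; run literally, its imputation step dilutes the treatment effect

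*SAP*

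**What the plan says.** SAP 2.5.4 sets out a multiple-imputation check on the primary result. On the assumption and the number of imputations it says: "This sensitivity analysis would first create multiple (100) imputations of missing NT-proBNP values under a MAR assumption". On the model it says: "The imputation model assumes a multivariate normal model for the 3 NT-proBNP measurements at baseline, Week 4 and Week 8". Patients without a baseline stay out: "Baseline value will not be imputed". Deaths are treated separately, "besides the imputation with 0 for the NT-proBNP values after death"; the sentence that holds this clause is incomplete. After imputation, "To the resulting 100 datasets, the original analysis model described above will be fitted". That analysis model (SAP 2.5.2 and 5.4.1) contains treatment, in/out-of-hospital status, gender, LVEF category, age and log baseline NT-proBNP.

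The section does not say whether imputation is run within arm or on pooled arms, and it does not state the scale of the normal model. Protocol 12.4.3 mentions multiple imputation without giving a model.

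Both documents schedule a Week 1 sample. In SAP 2.11, NT-proBNP is "measured in all subjects using the central laboratory at Visits 2 (randomization), 3, 5, and 7 (Weeks 0, 1, 4, and 8 respectively"); Protocol 8.3.3 lists the same visits.

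The primary analysis (SAP 2.5.3) and sensitivity analyses 2 to 4 (SAP 2.5.5 to 2.5.7) do not impute.

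**The concern.** An imputation model should contain at least what the analysis model contains, above all the effect being estimated. Here the analysis estimates a treatment difference, while the imputation model as listed has no treatment term. A patient with neither Week 4 nor Week 8 would be imputed from baseline alone, around a line averaged over both arms. Those patients carry no treatment difference, so the estimate moves toward a ratio of 1 even when data are missing completely at random. A check built on missing at random should not do that.

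The Week 1 value raises a separate issue. For a patient who leaves between Weeks 1 and 4, it may be the only post-randomization measurement. Without it, missing at random has to hold given baseline alone.

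At stake is the reading of the one analysis meant to show that missing data do not drive the primary result. A shift from 0.77 to 0.80 could be taken as sensitivity to missing data when it comes from the imputation model. Two programmers could also obtain different answers from the same text.

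**Working it through.** **Inputs from the documents.** 450 patients, 1:1; log effect -0.2614 (ratio 0.77); SD of the log change 0.85; two-sided 0.05; 15% missing (SAP section 3). The SAP and the protocol summary define the 15% as missing at baseline or at both Weeks 4 and 8. Protocol 12.8 leaves baseline out of that definition.

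**The plan's own figure.** Evaluable per arm: 225 × 0.85 = 191.25, taken as 191. Then 0.2614 / (0.85 × √(2/191)) = 3.005, and power = Φ(3.005 − 1.96) = 85.2% (85.0% with the noncentral t). In reverse, 190 per arm are needed, and 380 / 0.85 = 447.1, so 448 against the planned 450. The stated 85% reproduces. The SAP gives no figure for the imputation analysis itself.

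**Closed form.** Let a share m in each arm lack both visits and be imputed from baseline with no arm term. The baseline-adjusted difference is the full effect δ in the observed share (1 − m) and 0 in the imputed share, so the expected log effect is δ × (1 − m).

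| m | log effect | ratio |
|---|---|---|
| 0 | -0.2614 | 0.770 |
| 5% | -0.2483 | 0.780 |
| 10% | -0.2353 | 0.790 |
| 15% | -0.2222 | 0.801 |

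**Simulation, missing completely at random.** 450 patients, 200 trials, 10 imputations each, ANCOVA on treatment and log baseline, 15% missing both visits and 10% missing one. The following are assumptions, not taken from the documents:
- imputation on the log scale, and no deaths;
- correlations: baseline with Week 1 0.75, baseline with Weeks 4/8 0.62, Week 1 with Weeks 4/8 0.8, Week 4 with Week 8 0.8;
- 70% of the effect present at Week 1.

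The log SD of 0.98 comes from the phase 2 confidence interval in Protocol 1.1: ln(914/670) / 3.92 × √154 = 0.98, assuming 154 per arm (308 / 2).

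| Analysis | log effect | ratio |
|---|---|---|
| Complete cases | -0.264 | 0.768 |
| Baseline, Weeks 4 and 8 only (literal) | -0.221 | 0.802 |
| Week 1 added, no arm | -0.246 | 0.782 |
| Arm added, no Week 1 | -0.265 | 0.767 |
| Arm and Week 1 added | -0.266 | 0.766 |

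The Monte Carlo SE of the log effect is about 0.005. The literal model agrees with the closed form. The arm term alone removes the pull; Week 1 without arm removes only part of it. With 5% missing both visits, the literal model gives 0.783. At 15%, the rejection rate is 0.96 for complete cases and 0.90 for the literal model; both exceed 85% because the analysis adjusts for baseline.

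**Missingness dependent on the Week 1 change** (same set-up): complete cases 0.780, literal 0.813, arm only 0.780, arm and Week 1 0.773. With arm in the model, Week 1 recovers most of the remaining bias, which is small.

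**Precision from Week 1.** A second simulation used 400 trials, log SD 1.0, correlations 0.65 to 0.85 and a Week 1 log effect of -0.15. Under missing completely at random the literal model gave -0.225, against -0.264 with no missing data. With treatment in the model, adding Week 1 cut the SE from 0.0734 to 0.0712: 1 − 0.0712/0.0734 = 3%. When missingness followed the Week 1 change, arm only gave -0.255 and arm with Week 1 gave -0.260, against -0.258 with no missing data.

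**The case against.** The strongest reply is that the SAP is silent on arm and does not say the arms are pooled. If the program imputes by arm, the dilution disappears. That stands, and it makes the dilution conditional. It does not dispose of the point: the section lists the variables of its model, and the arm is not among them.

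The size also has limits. Patients without a baseline are not imputed, and values after death are set to zero instead of being drawn from the model. The share imputed at both visits is therefore likely below 15%.

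Week 1 is scheduled for everyone, not necessarily measured in everyone. SAP 2.11 excludes samples from patients who withdrew consent, and under pandemic limits Protocol 8.3.3 asks for alternative collection only for the Week 4 and 8 biomarkers. Some early leavers may have no Week 1 result.

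It can be argued that patients who stop treatment lose benefit, so that under the treatment-policy strategy an estimate nearer 1 is reasonable. The literal model is no test of that idea: it removes the treatment difference from every patient missing both visits, including those whose samples were merely unevaluable, while labelled missing at random. What does stand is that by-arm imputation from baseline alone nearly repeats the available-data result (0.767 against 0.768) and so tests little. That is a reason to bring in Week 1 and the covariates.

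Finally, this is a supportive analysis. The primary analysis is untouched, and dilution toward 1 does not create a false positive.

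**Conclusion.** The imputation model in SAP 2.5.4 is under-specified and, run literally, inconsistent with the analysis it feeds. With arms pooled, the imputation component shrinks the log effect by about the share of patients imputed at both visits: from 0.77 to about 0.78, 0.79 and 0.80 at 5%, 10% and 15%, the last being an upper limit. This assumes equal shares in both arms, missingness unrelated to outcome, and imputation on the log scale. The sizes for Week 1 (about 3% in SE, and some residual bias if dropout follows early change) rest on assumed correlations.

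A reader might infer more than the documents support:
- **That the SAP pools the arms.** It does not say so.
- **That leaving out Week 1 causes the dilution.** With arm in the model and missingness unrelated to Week 1, leaving it out causes no bias.
- **That the check as a whole moves toward no difference.** Zero after death is the most favourable possible value and helps the arm with more deaths; the logarithm of the average is undefined when both values are zero. The net direction is therefore not fixed.

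**What to change.** In SAP 2.5.4, state that:
- imputation is run separately by randomized arm, or with treatment in the model;
- the model uses log-transformed NT-proBNP at baseline, Week 1 (where available), Week 4 and Week 8;
- the primary ANCOVA covariates (in/out-of-hospital status, gender, LVEF category and age) are in the imputation model.

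The incomplete sentence in the same paragraph should be finished so that it is clear how zeros after death enter the log-scale endpoint. The cost is a few lines of SAP text and a small change to the imputation program. No new data are needed, and the primary analysis is unchanged.
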